8. SAFETY ANALYSES

The safety analyses will be based on the Safety population, unless otherwise specified.

8.1. Adverse Events Analyses

Adverse events analyses including the analysis of adverse events (AEs), Serious (SAEs) and other significant AEs will be based on GSK Core Data Standards. The details of the planned displays are provided in Section 15.14: List of Data Displays.

8.1.1. Analyses for Injection Site Reaction Adverse Events from Study Drug Injection

Injection Site Reaction (ISR) adverse events of interest are those from study drug injections. For the summary of study drug ISR adverse events by visit and maximum severity (overall and by common ISRs): ISRs will be assigned based on onset date to the most recent planned IM injection visit prior or equal to the AE onset date.

Maximum grade at each visit will be derived as the maximum grade among ISRs assigned to the particular visit, with consideration for whether the summary applies to a particular preferred term (vs. across preferred terms), drug-related associated to CAB and/or RPV, or stratification by subgroup (such as needle length, refer to Section 5.4.2).

Drug-related ISRs (based on investigator discretion) from study drug injections will be attributed to the causal agent (CAB vs. RPV) when this can be determined specifically based on the side of injection administration and the side of the reported ISR (as collected in the eCRF). If we are unable to determine the causal agent in those cases where both drugs are given on one side and the ISR is reported non-specifically, then the attribution to a specific causal agent will remain unknown.

Common study drug ISR adverse events are defined by MedDRA preferred terms including injection site pain, injection site induration, injection site nodules and preferred terms of any other ISR with $\geq 5\%$ participants in either treatment arm, coming from study drug injections. The same set of common terms will be applied to 'overall' (CAB and/or RPV), CAB alone, RPV alone.

Study drug ISRs will be attributed to the needle length (≤ 1.5 , >1.5 to <2 , ≥ 2 inches) specifically based on the side of injection administration and the side of the reported ISR (as collected in the eCRF). If we are unable to determine the needle length for events where both drugs are given on one side and their needle lengths are different, then the attribution to a needle length will remain unknown.

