5. CONSIDERATIONS FOR DATA ANALYSES AND DATA HANDLING CONVENTIONS

5.1. Study Treatment & Sub-group Display Descriptors

Treatment Group Descriptions			
RandAll NG Randomization System		Data Displays for Reporting	
Code	Description	Description	Order in TLF
A	Q8W	Q8W	1
B	Q4W	Q4W	2
C/A	Oral followed by Q8W	Q8W	1
C/B	Oral followed by Q4W	Q4W	2

Notes:

- Unless stated otherwise, data displays will present two treatment group columns (Q8W and Q4W), where treatment sequence C/A is pooled with sequence A and treatment sequence C/B is pooled with sequence B. The detailed treatment sequence descriptors (i.e. C/A and C/B) may be used in selected data listings. Treatment C refers to oral CAB + oral RPV, used for oral lead-in for subjects entering the study with no prior CAB+RPV exposure.

Treatment comparisons will be displayed as follows using the descriptors as specified:

- Q8W vs Q4W

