15.3.5. Assessment Window for PK Concentration Data

For PK concentration data at the withdrawal/unscheduled/LTFU Month 1 visits during maintenance phase (after assignment to study phase per Table 14), the visit will be slotting to the analysis visit per the following steps:

- Identify the ‘last nominal visit’ with the PK pre-dose assessment performed prior to the visit to be slotted during the same study phase
- Identify the nominal visit corresponding to the next planned pre-dose PK assessment visit (excluding visits with storage PK collection), that is subsequent to the ‘last nominal visit’ with PK pre-dose assessment during the same study phase.
- If the nominal visit corresponding to next planned pre-dose PK assessment visit is prior to/at Week 48 visit, the PK assessment at the unscheduled/withdrawal/LTFU Month1 visit will be slotted to this nominal visit corresponding to next planned pre-dose PK assessment visit.
- Otherwise, the PK assessment at the unscheduled/withdrawal/LTFU Month1 visit will be slotted to the earliest nominal visit from the following:
 - Nominal visit corresponding to the next planned pre-dose PK assessment visit
 - The nominal visit of the next planned injection occurring on or after the date of the PK assessment during the same study phase

During maintenance phase, the planned nominal visits for PK Pre-dose are Week 4B, 8, 16, 24, 32, 40, 48, 96 for Q4W arm; and are Day 1, Week 4B, 8, 16, 24, 32, 40, 48, 96 for

Q8W arm while Day 1 is required only for those transitioning from ATLAS on Q4W injections and Week 4B is required only for participants transitioning from oral SOC and requiring oral CAB+RPV lead-in. In addition, the participants on Q8W arm have planned nominal visits at Week 9 and 41 for 1-week post-dose.

For participants requiring oral CAB+RPV lead-in, the planned injection visits are Week 4B, Week 8, continuing every 4 weeks for Q4W arm and continuing every 8 weeks for Q8W arm. For participants not requiring oral CAB+RPV lead-in, the planned injection visits are every 4 weeks starting from Day 1 for Q4W arm and every 8 weeks starting from Day 1 for Q8W arm.

Example 1: If a participant on Q8W arm has the ‘last nominal visit’ (with PK pre-dose assessment) at Week 24 and then withdraws around Week 28, with the last injection at Week 24 and a Maintenance Phase PK assessment labelled at ‘LTFU Month 1’, This PK assessment labelled as ‘LTFU Month 1’ will be slotted to the subsequent planned nominal visit of Week 32.

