
Timeliness of Injections relative to Date of Projected Dosing Visits are assessed by using "actual injection visit date - projected visit date from first injection". The injections of interest in adherence analysis are those after first injection. For participants requiring the oral CAB+RPV lead-in, the first injection is planned to be taken at Week 4B. For participants not requiring the oral CAB+RPV lead-in, the first injection is planned to be taken at Baseline/Day 1. Each injection visit is counted only once. Individual CAB and RPV injections administered at the same visit are not counted twice. "Extra" unscheduled injections are excluded from all derivations. For example, if during a scheduled visit a participant receives 1 ml of injection instead of 2 ml due to a dosing error, but this participant returns one week later for the remaining 1 ml injection, then the additional visit is excluded. If a participant receives an extra injection at an unscheduled visit by mistake, this visit will also be excluded.
 
The categories of Timeliness of Injections relative to Date of Projected Dosing Visits for summary are listed below:
 
 < -14 days -14 to -8 days -7 to -4 days -3 to -2 days -1 0 day 1 2 to 3 days 4 to 7 days 8 to 14 days >14 days Missed Injection without Oral Bridging Missed Injection with Oral Bridging
Columbia Suicide Severity Rating Scale (C-SSRS)

 • Missing data will not have any imputation performed (Nilsson et al, 2013).

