No. in W48	No. in W96	No. in EOS	Population	IDSL / Example Shell	Title	Programming Notes	Deliverable
3.30	3.35	NA	Safety	201585/primary_02/T3.46	Summary of Study Drug Injection Site Reaction Adverse Events by Visit and Maximum Severity – Overall and Common (Maintenance Phase)	Change the second footnote to 'Note: Common ISR includes pain, induration, nodules and any other ISR with >=5% subjects in either treatment arm.' Footnote may be adjusted for clarifications.	W48, W96
3.31	3.36	NA	Safety	201585/primary_02/T3.47	Summary of Drug-related Study Drug Injection Site Reaction Adverse Events (Event-level Summary) - CAB (Maintenance Phase)		W48, W96
3.32	3.37	NA	Safety	201585/primary_02/T3.48	Summary of Drug-related Subject-level Characteristics of Study Drug Injection Site Reaction Adverse Events (Maintenance Phase) - Overall and Common (CAB)		W48, W96
3.33	3.38	NA	Safety	201585/primary_02/T3.49	Summary of Overall and Common Drug-related Study Drug Injection Site Reaction Adverse Events by Visit and Maximum Severity (Maintenance Phase) - CAB	Footnote may be adjusted for clarifications.	W48, W96
3.34	3.39	NA	Safety	201585/primary_02/T3.50	Summary of Maximum Drug-related Study Drug Injection Site Reaction Adverse Event Grade by Needle Length (Maintenance Phase) – Common (CAB)	Update the needle length in column header to be '<=1.5 inches', '>1.5 to <2 inches' and '>=2 inches' respectively. Change the first footnote to 'Note: Common ISR includes pain, induration, nodules and any other ISR with >=5% subjects in either treatment arm.'. Remove the second footnote.	W48, W96

Safety Tables							
No. in W48	No. in W96	No. in EOS	Population	IDSL / Example Shell	Title	Programming Notes	Deliverable
3.35	3.40	NA	Safety	201585/primary_02/T3.51	Summary of Drug-related Study Drug Injection Site Reaction Adverse Events (Event-level Summary) - RPV (Maintenance Phase)		W48, W96
3.36	3.41	NA	Safety	201585/primary_02/T3.52	Summary of Drug-related Subject-level Characteristics of Study Drug Injection Site Reaction Adverse Events (Maintenance Phase) - Overall and Common (RPV)		W48, W96
3.37	3.42	NA	Safety	201585/primary_02/T3.53	Summary of Overall and Common Drug-related Study Drug Injection Site Reaction Adverse Events by Visit and Maximum Severity (Maintenance Phase) - RPV	Footnote may be adjusted for clarifications.	W48, W96

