15.14.5.5. Safety Figures

Note: Unless otherwise specified, display both arms.

Safety Figures							
No. in W48	No. in W96	No. in EOS	Population	IDSL / Example Shell	Title	Programming Notes	Deliverable
3.1	3.1	NA	Safety	201585/primary_02/F3.1	Plot of Common Adverse Events and Relative Risk - Q8W vs. Q4W (Maintenance Phase) – Excluding Study Drug ISRs	Remove the second footnote.	HL, W48, W96
3.2	3.2	NA	Safety	201585/primary_02/F3.1	Plot of Common Study Drug Injection Site Reaction Adverse Events and Relative Risk - Q8W vs. Q4W (Maintenance Phase)	Remove the second footnote.	HL, W48, W96
3.3	3.3	NA	Safety	201585/primary_02/F3.5	Plot of Onset, Duration, and Severity of Overall and Common Study Drug Injection Site Reaction AEs by Maximum Grade — CAB and/or RPV (Maintenance Phase)		W48, W96
3.4	3.4	NA	Safety	201585/primary_02/F3.6	Plot of Onset, Duration, and Severity of Overall and Common Drug-related Study Drug Injection Site Reaction AEs by Maximum Grade — CAB (Maintenance Phase)		W48, W96
3.5	3.5	NA	Safety	201585/primary_02/F3.7	Plot of Onset, Duration, and Severity of Overall and Common Drug-related Study Drug Injection Site Reaction AEs by Maximum Grade — RPV (Maintenance Phase)		W48, W96
3.6	3.6	NA	Safety	201585/primary_02/F3.8	Plot of Incidence of Maintenance Phase Study Drug Injection Site Reaction Adverse Events by Visit (Overall and Common) – CAB and/or RPV	Footnote may be adjusted for clarifications.	W48, W96
3.7	3.7	NA	Safety	201585/primary_02/F3.9	Plot of Incidence of Maintenance Phase Drug-Related Study Drug Injection Site Reaction Adverse Events by Visit (Overall and Common) – CAB	Footnote may be adjusted for clarifications.	W48, W96

Safety Figures							
No. in W48	No. in W96	No. in EOS	Population	IDSL / Example Shell	Title	Programming Notes	Deliverable
3.8	3.8	NA	Safety	201585/primary_02/F3.10	Plot of Incidence of Maintenance Phase Drug-Related Study Drug Injection Site Reaction Adverse Events by Visit (Overall and Common) – RPV	Footnote may be adjusted for clarifications.	W48, W96
3.9	3.9	NA	Safety	201585/primary_02/F3.11	Plot of Incidence of Grade 3-5 Maintenance Phase Study Drug Injection Site Reaction Adverse Events by Visit (Overall and Common) - CAB and/or RPV	Footnote may be adjusted for clarifications.	W48, W96

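### By-visit injection site reaction displays pool prior-exposure strata, so the Day 1 to Week 8 pattern and the Week 4B arm difference are confounded by who is injected

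*SAP*

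**What the plan says.** SAP Section 8.1.1 gives the rule for the by-visit summaries: "ISRs will be assigned based on onset date to the most recent planned IM injection visit prior or equal to the AE onset date". The only subgroup it names for these summaries is needle length, given as an example.

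The injection visits are set out in Section 15.3.5. One sentence covers those who take the lead-in: "For participants requiring oral CAB+RPV lead-in, the planned injection visits are Week 4B, Week 8, continuing every 4 weeks for Q4W arm". Their Q8W counterparts move to 8-week spacing after Week 8. For everyone else, "the planned injection visits are every 4 weeks starting from Day 1 for Q4W arm and every 8 weeks starting from Day 1". The second interval there is that of the Q8W arm. Section 15.6.4 agrees: "For participants requiring the oral CAB+RPV lead-in, the first injection is planned to be taken at Week 4B". Section 5.1 identifies who takes the lead-in; the oral treatment is "used for oral lead-in for subjects entering the study with no prior CAB+RPV exposure". The Q8W schedule in Section 15.2.2 marks the Week 4B column as applying to oral lead-in participants only.

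Section 5.1 also sets the default display: two columns, with lead-in and non-lead-in sequences pooled within arm. Table 3.30 in Section 15.14.5.4 is titled "Summary of Study Drug Injection Site Reaction Adverse Events by Visit and Maximum Severity", and Figure 3.6 in Section 15.14.5.5 "Plot of Incidence of Maintenance Phase Study Drug Injection Site Reaction Adverse Events by Visit (Overall and Common". Neither these nor Tables 3.33 and 3.37 and Figures 3.7-3.11 name a stratum in title or programming note. The Week 96 counterparts are Tables 3.35, 3.38 and 3.42 and the same figure numbers.

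**The concern.** A by-visit plot with one line per arm invites two readings: how ISR incidence changes as treatment continues, and how the arms differ at each visit. Both require the same kind of participant to stand behind successive points and behind the two lines. At the first visits this fails by design. A rise from Day 1 to Week 4B can arise because experienced recipients are followed by first-time recipients. An arm gap at Week 4B can arise because Q4W includes continuing recipients there and Q8W does not.

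The Week 4B gap deserves particular care. Up to and including that visit, lead-in participants in both arms follow the same planned course: oral lead-in, then a first injection. The dosing interval has not yet differed for them. ISRs are a listed adverse event of special interest with their own analysis section, and these displays are Week 48 and Week 96 deliverables in which arms will be compared over time.

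**Working it through.** **Step 1: who has a planned injection at each visit** (Sections 15.2.2, 15.3.5, 15.6.4)

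| Visit | Q8W | Q4W |
|---|---|---|
| Day 1 | prior-exposed only | prior-exposed only |
| Week 4B | lead-in only, first injection | lead-in (first injection) and prior-exposed (continuing) |
| Week 8 | both strata | both strata |
| Later planned visits of the arm | both strata | both strata |

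Composition changes only across Day 1, Week 4B and Week 8. In Q4W it is already settled at Week 4B.

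**Step 2: inputs.** The SAP states no figure to reproduce. It gives neither ISR rates, nor the share of prior-exposed participants, nor the denominator; the shells are held outside the SAP. The following are assumptions:
- q = share prior-exposed, 25-50%, equal in both arms
- r1 = ISR rate at a first injection, 60-70%
- r2 = ISR rate at later injections, 30-40%
- no true regimen difference

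**Step 3: denominator = participants injected at the visit.**
- Day 1: r2 in both arms.
- Week 4B, Q8W: r1.
- Week 4B, Q4W: (1-q)·r1 + q·r2.
- Difference Q8W-Q4W: r1 - [(1-q)·r1 + q·r2] = q·(r1-r2).

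Smallest case, q = 0.25, rates 60/40%: 0.25 × 0.20 = +5 points. Largest case, q = 0.50, rates 70/30%: 0.50 × 0.40 = +20 points. If r1 = r2 the difference is 0. Example with q = 0.35 and 70/30%: Day 1 is 30% in both arms; Week 4B is 70% in Q8W against 0.65 × 70 + 0.35 × 30 = 56% in Q4W, a gap of 14 points.

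**Step 4: denominator = whole Safety arm.**
- Week 4B, Q8W: (1-q)·r1.
- Week 4B, Q4W: (1-q)·r1 + q·r2.
- Difference: -q·r2.

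Over the same ranges this runs from 0.25 × 30 = 7.5 to 0.50 × 40 = 20 points, with Q8W the lower arm. It is not zero even when r1 = r2. Example with q = 0.35 and 70/30%: 45.5% against 56%, a difference of -10.5 points.

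**Step 5: time pattern from composition alone.** Suppose the strata differ persistently (70% without prior exposure, 30% with) and nobody's rate changes. With q = 0.35 and the injected-at-visit denominator, Day 1, Week 4B and Week 8 read 30%, 70%, 56% in Q8W and 30%, 56%, 56% in Q4W. The movement is entirely a change in who is counted.

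**Step 6: within strata.** Under the Step 2 assumptions, participants without prior exposure show r1 in both arms at Week 4B, a difference of 0. Prior-exposed participants have a Week 4 injection only in Q4W, so no arm comparison exists for them at that visit.

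**The case against.** The strongest reply is that these are descriptive displays with no test, margin or decision attached. Randomization is stratified by prior exposure, so the whole-phase ISR summaries (Tables 3.28 and 3.29) are balanced on this factor in expectation. Section 8.1.1 offers needle length only as an example of a subgroup and refers to Section 5.4.2, which lists prior exposure. The non-population listings are shown by prior exposure, and footnotes may be adjusted for clarification. The assignment rule itself is sound and would not change.

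Most of this stands, and it limits the weight of the point. What does not follow is that the plan already covers it. The wording permits stratification but does not commit to it, and where stratified displays are intended the list says so, as in the PK tables and figures and the ISR box plot, Figure 5.10. A listing does not correct the reading of a pooled curve.

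A fair objection also applies to the remedy: a panel for at least 1 week of exposure merges 1-24 with more than 24 weeks, and Section 15.6.2 counts exposure from the start of oral CAB. Some participants in that panel may have had few injections. The three-level split reduces this.

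**Conclusion.** The point holds in limited form. In the pooled by-visit ISR displays, the Day 1, Week 4B and Week 8 pattern and the Week 4B arm difference are confounded by composition. The structure follows from the SAP alone; the size does not. The range of +5 to +20 points rests on the assumed rates and shares and on counting only those injected at the visit. With the whole Safety arm as denominator the same assumptions give -7.5 to -20 points. Section 15.1.1's deviation examples imply different volumes at Week 4B for lead-in participants and at continuing Q4W injections, so equal rates should not be taken for granted, but that does not supply a rate.

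A reader might infer three stronger things that the document does not support:
- That the whole ISR time trend is built in. From Week 8 both strata are injected at every planned visit of their arm, so a decline after that is not produced by this mechanism.
- That Q8W will show more ISRs at Week 4B. The direction depends on a denominator the SAP does not state, and with injected participants as denominator the gap vanishes if r1 = r2.
- That the overall ISR comparison between arms is biased. Stratified randomization protects it, and no formal conclusion depends on the by-visit displays.

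This is worth correcting before the displays are produced, but it does not threaten a trial conclusion.

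**What to change.** - Produce Week 48 Tables 3.30, 3.33, 3.37 and Figures 3.6-3.11, and their Week 96 counterparts, by rederived prior exposure: 0 against at least 1 week, or 0, 1-24 and more than 24 weeks. Both groupings are already defined in Section 5.4.2.
- State in Section 8.1.1 that the denominator is participants injected at that visit, and show that number per arm and visit.
- Note that prior-exposed Q8W participants have no Week 4 injection, so the Week 4B arm comparison exists only in the 0-week stratum.
- A pooled version may be kept, with a footnote on its composition at Day 1 and Week 4B.

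The cost is SAP wording, more output pages and smaller numbers per panel. No new data are required, and the rule assigning ISRs to visits can stay as it is.

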8.2. Adverse Events of Special Interest Analyses

Adverse events of special interest (AESI) are determined for CAB and/or RPV based on pre-clinical and clinical experience, along with information for the Integrase Inhibitor class of HIV medications and RPV safety profile. Table 4 shows the currently identified AESI, drug(s) of Interest and the reasons for inclusion. Changes to the MedDRA dictionary may occur between the start of the study and the time of reporting, and/or

emerging data from on-going studies may highlight additional adverse events of special interest, therefore the list of AESIs may change at the time of reporting.

A summary by system organ class and preferred term will be provided for each of AESI. The characteristics of event occurrences during the maintenance phase will be summarized for common AESI which have at least 20 participants in either treatment arm. For Depression, anxiety and suicidal ideation/behaviour AESI, a summary by system organ class, maximum DAVIDS toxicity grade and prior history of suicidal ideation will be provided. The details of the planned grouping and planned displays are provided in Section 15.11 and Appendix 14: List of Data Displays.

Table 4 Adverse Events of Special Interest

Adverse Events of Special Interest	Drug(s) of Interest	Reason for Inclusion
Hepatic Safety Profile: Assessment of Risk of hepatotoxicity	CAB+RPV	Clinical, Class, Regulatory Interest, More prevalent in HIV population
Hypersensitivity Reactions (HSR)	CAB	Class, Regulatory Interest, Occurs in HIV population
Rash	RPV	Class, Regulatory Interest, Occurs in HIV population
Prolongation of the Corrected QT Interval of the ECG in Supratherapeutic Doses	RPV	Non-clinical, Clinical, Regulatory Interest
Suicidal Ideation/Behaviour	CAB+RPV	Clinical, Class, Regulatory Interest, More prevalent in HIV population
Depression	CAB+RPV	Clinical, Class, Regulatory Interest, More prevalent in HIV population
Bipolar Disorder	CAB+RPV	Clinical, Class, Regulatory Interest, More prevalent in HIV population
Psychosis	CAB+RPV	Clinical, Class, Regulatory Interest, More prevalent in HIV population
Mood Disorders	CAB+RPV	Clinical, Class, Regulatory Interest
Anxiety	CAB+RPV	Clinical, Class, Regulatory Interest
Sleep Disorders	CAB+RPV	Clinical, Class, Regulatory Interest, More prevalent in HIV population
Injection Site Reactions (ISR) from Study Drug Injections [1]	CAB+RPV	Clinical

Adverse Events of Special Interest	Drug(s) of Interest	Reason for Inclusion
Seizures and Seizure-like Events	CAB	Clinical, Regulatory Interest
Weight Gain	CAB	Clinical, Class
Rhabdomyolysis	CAB	Clinical, Class
Pancreatitis	CAB	Clinical, Therapeutic Area, More prevalent in HIV population
Impact on Creatinine	CAB+RPV	Regulatory Interest, Therapeutic Area, More prevalent in HIV population
Safety in Pregnancy	CAB	Regulatory Interest, Class
NOTE: [1] A separate analysis will be performed for ISRs from study drug injections as described in Section 8.1.1.		

8.3. Clinical Laboratory Analyses

Laboratory evaluations including the analysis of results of Chemistry laboratory tests, Haematology laboratory tests, Urinalysis, and liver function tests will be based on GSK Core Data Standards. The details of the planned displays are in [Appendix 14: List of Data Displays](#).

